**Table 2. Local Reaction Grading Scale**

	Mild (Grade 1)	Moderate (Grade 2)	Severe (Grade 3)a	Potentially Life-Threatening (Grade 4)b
Pain at the injection site	Does not interfere with activity	Repeated use of nonnarcotic pain reliever >24 hours or interferes with activity	Any use of narcotic pain reliever or prevents daily activity c	Emergency room visit or hospitalization for severe pain at the injection site
Redness	>2.0 cm to 5.0 cm (5 to 10 measuring device units)	>5.0 cm to 10.0 cm (11 to 20 measuring device units)	>10.0 cm ( $\geq 21$ measuring device units)	Necrosis or exfoliative dermatitis
Swelling	>2.0 cm to 5.0 cm (5 to 10 measuring device units)	>5.0 cm to 10.0 cm (11 to 20 measuring device units)	>10.0 cm ( $\geq 21$ measuring device units)	Necrosis

- a. Participants experiencing  $\geq$  Grade 3 local reactions are to be seen by the study site. Refer to the Unscheduled Visits section of the protocol for further guidance.
- b. Grade 4 assessment should be made by the investigator. Grade 4 will not be collected in the e-diary but will be recorded as an AE on the CRF.
- c. Prevents daily activity, ie, results in missed days of work or school or is otherwise incapacitating, or includes use of narcotics for analgesia.

Only an investigator is able to classify a participant's local reaction as Grade 4, after physical examination of the participant or documentation from another medically qualified source (eg, emergency room or hospital record), or, in the case of pain at the injection site only, telephone contact with the participant. If a participant experiences a Grade 4 local reaction, the investigator must immediately notify the sponsor.

### **Presence or Absence**

The presence or absence of each local reaction (pain at the injection site, redness, and swelling) on a given day is defined as follows:

- = Missing, if the value is missing on a given day;
- = “Yes,” if the participant reports the reaction as “yes” for redness or swelling or “mild,” “moderate,” “severe,” or “Grade 4”(as per physical examination by a physician) for pain at the injection site on a given day;
- = “No,” if the participant reports the reaction as “no” for redness or swelling or “none” for pain at the injection site on a given day.

For each local reaction and any local reaction on any day, Table 3 details the algorithm to derive the presence of a reaction (yes or no) during the interval from Day 1 through Day 7.

**Table 3. Derived Variables for Presence of Each and Any Local Reaction Within 7 Days**

Variable a	Yes (1)	No (0)	Missing (.)
Presence of each local reaction.	Participant reports the reaction as “yes” on any day (Day 1 through Day 7).	Participant reports the reaction as “no” on all 7 days (Day 1 through Day 7) or as a combination of “no” and missing on all 7 days (Day 1 through Day 7).	Participant does not report any data on all 7 days (Day 1 through Day 7).
Presence of any local reaction.	Participant reports any local reaction as “yes” on any day (Day 1 through Day 7).	For all 3 local reactions, participant reports “no” on all 7 days (Day 1 through Day 7) or as a combination of “no” and missing on all 7 days (Day 1 through Day 7).	Participant does not report any data for all 3 local reactions on all 7 days (Day 1 through Day 7).

a. The variables will be derived for each and any of the local reactions (redness, swelling, and pain at the injection site) within the interval from Day 1 through Day 7 after vaccination.

### **Severity and Maximum Severity**

For each local reaction reported, the maximum severity grade will be derived for the e-diary collection period (Day 1 through Day 7) as follows:

Maximum severity grade

- = Missing, if values are missing for all days (Days 1-7);
- = 0, if the participant reports all reactions as “no” or a combination of missing and “no” for all days (Days 1-7);
- = *Highest grade* (maximum severity) within 7 days after vaccination, if the answer is not “no” for at least 1 day.

### **Duration (First to Last Day Reported)**

The duration of each local reaction will be calculated in days as (resolution date of reaction - start date of reaction + 1). Resolution of the event is the last day on which the event is recorded in the e-diary or the date the event ends if it is unresolved during the participant diary-recording period (end date collected on the CRF), unless chronicity is established. If there is no known end date, the duration will be considered unknown and set to missing. Participants with no reported reaction have no duration.

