**Table 4. Systemic Event Grading Scale**

	Mild (Grade 1)	Moderate (Grade 2)	Severe (Grade 3) a	Potentially Life-Threatening (Grade 4) b
Joint pain	No interference with activity	Some interference with activity	Significant; prevents daily activity c	Emergency room visit or hospitalization for severe joint pain

- a. Participants experiencing  $\geq$  Grade 3 systemic events are to be seen by the study site. Refer to the Unscheduled Visits section of the protocol for further guidance.
- b. Grade 4 assessment should be made by the investigator. Grade 4 will not be collected in the e-diary but will be collected as an AE on the CRF.
- c. Prevents daily routine activity, ie, results in missed days of work or school or is otherwise incapacitating or includes use of narcotics for analgesia.

The derivations for systemic events will be handled similarly to the way local reactions are handled for presence of the event, severity level, duration, and onset day. The variables associated with the systemic events will be computed similarly to the way local reactions are computed (see [Section 3.1.1.1](#)).

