##### **5.3.1.1. Reactogenicity Data**

For derived variables based on reactogenicity data, if any day of the 7-day e-diary is available, the “any day (Days 1-7)” data will be considered nonmissing.

The reactogenicity data are collected through the e-diary, which does not allow participants to skip the question. Therefore, for a specific day, as long as the e-diary data are transferred for that day, all of the reactogenicity data for the participant on that day will be considered nonmissing. No missing reactogenicity data will be imputed other than what is described in Section 3.1.1.

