## 6. ANALYSES AND SUMMARIES

### 6.1. Primary Endpoints

#### 6.1.1. Primary Safety Endpoints

##### 6.1.1.1. Local Reactions

###### 6.1.1.1.1. Main Analysis

- Estimand: The proportion of participants reporting local reactions (redness, swelling, and pain at the injection site) for up to 7 days following vaccination ([Section 3.1.1.1](#)).
- Estimand strategy: Treatment policy.
- Analysis set: Safety population ([Section 4](#)).
- Analysis time point: Day 1 through Day 7 after vaccination. Refer to [Section 3.1.1.1](#) for maximum severity.
- Analysis methodology: Descriptive summary statistics.
- Intercurrent events and missing data: The participants without any e-diary data throughout the 7 days after vaccination will be excluded from the analysis. For participants who discontinue, all collected data will be included; intermediate missing values will not be imputed.
- Reporting results: The proportion, the numerator (n) and denominator (N) used for the calculation of the proportion, and associated 2-sided Clopper-Pearson 95% CI will be presented, by vaccine group, for the following variables:
  - Presence or absence of each local reaction on each day (Day 1-7) after vaccination.
  - Presence or absence of each local reaction on “any day (Day 1-7)” after vaccination.
  - Presence or absence of any local reaction on “any day (Day 1-7)” after vaccination.
  - Maximum severity of each local reaction on “any day (Day 1-7)” after vaccination.

The n, mean, standard deviation, median, minimum, and maximum will be presented by vaccine group, for the following variables:

- Duration of each local reaction after vaccination.
- Onset day of each local reaction after vaccination.
- Onset day of any local reaction after vaccination.

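### Reactions whose stop date is never obtained drop out of the duration summaries, so mean and maximum duration can be understated

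*SAP*

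**What the plan says.** SAP 3.1.1.1 computes duration as resolution date minus start date plus 1. "Resolution of the event is the last day on which the event is recorded in the e-diary", or else the date the event ends "if it is unresolved during the participant diary-recording period (end date collected on the CRF), unless chronicity is established". It then adds: "If there is no known end date, the duration will be considered unknown and set to missing". The SAP does not say what follows once chronicity is established.

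SAP 3.1.1.2 has systemic events "handled similarly to the way local reactions are handled for presence of the event, severity level, duration, and onset day".

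SAP 5.3.1.1 closes off other handling: "No missing reactogenicity data will be imputed other than what is described in Section 3.1.1". SAP 6.1.1.1 lists "Duration of each local reaction after vaccination" among the variables summarised by n, mean, SD, median, minimum and maximum per vaccine group, and 6.1.1.2 does the same for systemic events. No censored-data summary of duration is planned.

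The protocol works to limit the gap. Section 8.2.1 obliges the site to contact the participant for the stop date of any reaction ongoing on the last completed diary day. Section 8.11.2 has those dates collected and entered in the CRF at Visit 2 (28 to 38 days after Visit 1). Section 8.2.2.3 has a Day 7 fever measured daily until it resolves.

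**The concern.** Whether a duration goes missing depends on the duration itself. A reaction that stops during the diary cannot be lost, while one still running when recording stops can be. The analysis then describes the durations that remain as if the absent ones were a random subset.

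The discarded reactions are not uninformative either. Each has a start date and a last date on which it was known to be present, so a minimum duration is known. SAP 6.1.1.1 includes all collected data for participants who discontinue, yet a woman who withdraws during a reaction contributes no duration at all.

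What is at stake is the description of tolerability under coadministration. An unusually long reaction is what a reader looks for in a duration table, and the maximum is the entry most easily lost.

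**Working it through.** The plan gives no figure for durations or missing stop dates, so there is nothing to reproduce. The check has four steps.

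**1. Which reactions can be lost**

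| Reaction | End date under SAP 3.1.1.1 | Duration |
|---|---|---|
| Ends while the diary is being completed | Last diary day recorded | Kept |
| Ongoing on last completed diary day, stop date in CRF | CRF date | Kept, however long |
| Ongoing on last completed diary day, no stop date obtained | None | Missing |
| Judged chronic | Not stated | Not stated |

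The last completed day need not be Day 7. If a participant stops the diary early during a reaction and no CRF date exists, the SAP does not say whether her last recorded day counts as resolution or the duration is missing.

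**2. Direction**

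For a given onset day, a reaction still ongoing at the end of the diary is longer than one that has already ended. Lost reactions are therefore longer on average, but not in every case. Onset on Day 7 with an end on Day 8 gives 8 − 7 + 1 = 2 days. Suppose 60 reactions, of which 55 have known durations averaging 2.5 days. Restoring five 2-day reactions gives (2.5 × 55 + 2 × 5)/60 = 2.46, slightly lower than 2.5.

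**3. Size of the effect on the mean (all inputs assumed)**

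- f = share of reactions ongoing at the end of the diary: 2% to 10%
- q = share of those with no stop date: 0 to 100%
- a = mean duration of reactions ending in the diary: 2 to 3 days
- b = mean duration of those outlasting it: 9 to 12 days

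True mean = (1 − f)a + fb. Reported mean = [(1 − f)a + f(1 − q)b]/(1 − fq).

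Example with f = 10%, q = 50%, a = 2, b = 12:
- true mean: 0.9 × 2 + 0.1 × 12 = 3.00
- reported mean: (1.8 + 0.6)/0.95 = 2.53
- bias: −0.47 day

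| q | Bias in the mean (days), over the ranges of f, a and b |
|---|---|
| 0 | 0 |
| 10% | −0.01 to −0.09 |
| 25% | −0.03 to −0.23 |
| 50% | −0.06 to −0.47 |
| 100% | −0.12 to −1.00 |

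**4. Median and maximum**

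A simulation used geometric durations, with onset on Day 1, 2 or 3 (probabilities 0.6, 0.3, 0.1). A reaction running past Day 7 lost its stop date with probability q.

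| True mean | Share past Day 7 | Reported mean at q = 10%, 50%, 100% | Median |
|---|---|---|---|
| 2 | 1.3% | 1.99, 1.96, 1.92 | 2, falling to 1 from q = 10% |
| 3 | 7.5% | 2.96, 2.76, 2.49 | 2 throughout |
| 4 | 15.8% | 3.90, 3.46, 2.81 | 3, falling to 2 only at q = 100% |

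The first row's shift is a boundary effect. With a true mean of 2 days, half of all durations are exactly 1 day, so removing a few long ones tips the median. Elsewhere it moves only when every stop date is lost. The maximum has no such protection: if the longest reaction is the one without a stop date, it disappears from the table.

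**The case against.** The strongest reply is that the protocol closes most of this gap. Sites must seek stop dates, Visit 2 collects them again, and Day 7 fevers are followed to resolution. Long reactions with a CRF date stay in and can set the maximum. Duration is a derived descriptive variable with no planned between-group comparison, and the primary safety estimands are proportions that do not use it. Presence on each of Days 1 to 7 is reported by group with confidence intervals, so excess prevalence at Day 7 under coadministration would be visible. The n beside each duration summary, set against the number reporting the reaction, shows how many durations are absent.

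All of that stands, and it makes the point small. It does not cover the residual cases for which the rule was written. Even with full site compliance, a reaction still ongoing at Visit 2 may have no end date at the interim analysis, which is run on Visit 2 data. Prevalence by day stops at Day 7, and the n does not show how long the dropped reactions had already lasted.

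A reader might infer that chronic reactions receive no duration. The text says only "unless chronicity is established", which leaves the handling open rather than stating an exclusion.

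**Conclusion.** A minor weakness, worth correcting because the correction is cheap. The rule makes missingness depend on duration and discards a known minimum, so the mean and especially the maximum can be understated. The size depends on how many stop dates remain unknown, which the documents do not give. The figures above rest on assumed inputs and serve only to show scale: hundredths of a day if follow-up mostly succeeds, up to about half a day if it fails for half of the ongoing reactions.

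Three stronger readings are tempting and are not supported:
- That reported durations are biased short as a matter of fact: the bias is zero if all stop dates are obtained, and an individual lost reaction may be short.
- That the summaries rest only on the shorter reactions: those with a CRF stop date are included whatever their length.
- That the primary safety results are affected: the proportions reporting reactions do not depend on end dates.

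**What to change.** In SAP 3.1.1.1, and by reference 3.1.1.2, replace the set-to-missing rule. A reaction with no known end date is kept with a minimum duration, the last date known ongoing minus start date plus 1, and flagged as censored. For example, a reaction starting on Day 5 and last known present on Day 7 is recorded as at least 7 − 5 + 1 = 3 days. State that the same rule covers a diary stopped early during a reaction, and say how the chronicity exception is handled under it.

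In SAP 6.1.1.1 and 6.1.1.2:
- show per vaccine group the number of reactions with an unknown end date or judged chronic;
- report the maximum as ≥ x days when the longest value is censored;
- retain the present mean, SD and median, labelled as based on reactions with known end dates.

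A Kaplan-Meier median is optional. The cost is SAP wording and a few lines of programming on data already collected. The small downside is that some table entries become lower bounds.

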### **Onset Day**

The onset day of each local reaction will be derived. Onset day is defined as the first day of reporting any severity.

For the onset day of each local reaction, if participants report a change in severity of the local reaction, only the first day of reporting that specific local reaction will be counted.

In summary, the following variables will be derived for local reactions:

1. Presence or absence of each local reaction on each day (Day 1-7) after vaccination.
2. Presence or absence of each local reaction on “any day (Day 1-7)” after vaccination.
3. Maximum severity of each local reaction on “any day (Day 1-7)” after vaccination.
4. Presence or absence of any local reaction on “any day (Day 1-7)” after vaccination.
5. Duration of each local reaction after vaccination.
6. Onset day of each local reaction after vaccination.
7. Onset day of any local reaction after vaccination.

### 3.1.1.2. Systemic Events

During the reactogenicity e-diary reporting period, participants will be asked to assess nausea/vomiting, diarrhea, headache, fatigue, muscle pain, and joint pain and to record the symptoms in the reactogenicity e-diary. The symptoms will be assessed by the participant as absent, mild, moderate, or severe according to the grading scale in Table 4.

Participants will also be instructed to contact site staff if they experience any possible Grade 4 prompted systemic event (ie, emergency room visit or hospitalization for nausea/vomiting, diarrhea, headache, fatigue, muscle pain, or joint pain) within 7 days after vaccination. Study staff may also contact the participant to obtain additional information on Grade 3 events entered into the e-diary.

Only an investigator is able to classify a participant's systemic event as Grade 4, after physical examination of the participant or documentation from another medically qualified source (eg, emergency room or hospital record) or telephone contact with the participant. If a participant experiences a Grade 4 systemic event, the investigator must immediately notify the sponsor. The procedure for notification of the sponsor is provided in the study documentation.

Further, if a systemic event persists beyond the end of the e-diary period following vaccination, the participant will be requested to report that information and/or any new AEs that develop to the investigator. The investigator will enter this additional information in the CRF.

**Table 4. Systemic Event Grading Scale**

	Mild (Grade 1)	Moderate (Grade 2)	Severe (Grade 3) a	Potentially Life-Threatening (Grade 4) b
Nausea/vomiting	No interference with activity or 1-2 times in 24 hours	Some interference with activity or >2 times in 24 hours	Prevents daily activity; requires IV hydration	Emergency room visit or hospitalization for hypotensive shock
Diarrhea	2-3 loose stools in 24 hours	4-5 loose stools in 24 hours	≥6 loose stools in 24 hours	Emergency room visit or hospitalization for severe diarrhea
Headache	No interference with activity	Repeated use of nonnarcotic pain reliever >24 hours or some interference with activity	Significant; any use of narcotic pain reliever or prevents daily activity c	Emergency room visit or hospitalization for severe headache
Fatigue/tiredness	No interference with activity	Some interference with activity	Significant; prevents daily activity c	Emergency room visit or hospitalization for severe fatigue
Muscle pain	No interference with activity	Some interference with activity	Significant; prevents daily activity c	Emergency room visit or hospitalization for severe muscle pain

**Table 4. Systemic Event Grading Scale**

	Mild (Grade 1)	Moderate (Grade 2)	Severe (Grade 3) a	Potentially Life-Threatening (Grade 4) b
Joint pain	No interference with activity	Some interference with activity	Significant; prevents daily activity c	Emergency room visit or hospitalization for severe joint pain

- a. Participants experiencing  $\geq$  Grade 3 systemic events are to be seen by the study site. Refer to the Unscheduled Visits section of the protocol for further guidance.
- b. Grade 4 assessment should be made by the investigator. Grade 4 will not be collected in the e-diary but will be collected as an AE on the CRF.
- c. Prevents daily routine activity, ie, results in missed days of work or school or is otherwise incapacitating or includes use of narcotics for analgesia.

The derivations for systemic events will be handled similarly to the way local reactions are handled for presence of the event, severity level, duration, and onset day. The variables associated with the systemic events will be computed similarly to the way local reactions are computed (see [Section 3.1.1.1](#)).

### 3.1.1.3. Fever

Oral temperature will be collected in the reactogenicity e-diary in the evening daily during the reactogenicity e-diary reporting period. It will also be collected at any time during the reactogenicity e-diary data collection period when fever is suspected. Fever is defined as an oral temperature of  $\geq 100.4^{\circ}\text{F}$  ( $\geq 38.0^{\circ}\text{C}$ ). The highest temperature for each day will be recorded in the reactogenicity e-diary. Temperature will be measured and recorded to 1 decimal place. Fever will be grouped into ranges for the analysis according to Table 5.

In the event of a fever on Day 7, temperature will be collected daily until the fever has resolved (1 day of temperature  $< 100.4^{\circ}\text{F}$  [ $< 38.0^{\circ}\text{C}$ ]) in order to collect a stop date in the CRF. A participant with a fever  $\geq 102.1^{\circ}\text{F}$  ( $\geq 39.0^{\circ}\text{C}$ ) will be prompted to contact the investigator to assess the fever and perform an unscheduled visit as appropriate. Study staff must also contact the participant to obtain additional information if a temperature of  $\geq 102.1^{\circ}\text{F}$  is entered into an e-diary.

**Table 5. Scale for Fever**

100.4°F to 101.1°F ( $\geq 38.0^{\circ}\text{C}$ to $38.4^{\circ}\text{C}$ )
101.2°F to 102.0°F ( $> 38.4^{\circ}\text{C}$ to $38.9^{\circ}\text{C}$ )
102.1°F to 104.0°F ( $> 38.9^{\circ}\text{C}$ to $40.0^{\circ}\text{C}$ )
$> 104.0^{\circ}\text{F}$ ( $> 40.0^{\circ}\text{C}$ )

Note: Fever is defined as an oral temperature  $\geq 100.4^{\circ}\text{F}$  ( $\geq 38.0^{\circ}\text{C}$ ).

### 3.1.1.4. Use of Antipyretic Medication

The use of antipyretic medication to treat symptoms associated with study interventions will be recorded in the reactogenicity e-diary daily during the reporting period (Day 1 through Day 7).

For the use of antipyretic medication from Day 1 through Day 7, the following endpoints and variables will be derived for analysis following the same rules as for local reactions (see [Section 3.1.1.1](#)), where applicable:

- Presence (yes or no) of use of antipyretic medication on each day (Day 1-7).
- Presence (yes or no) of use of antipyretic medication on any day (Day 1-7).
- Duration (first to last day reported) of use of antipyretic medication.
- Onset day of use of antipyretic medication.

The use of antipyretic medication will be summarized and included in the systemic event summary tables but will not be considered a systemic event.

### 3.1.1.5. Adverse Events

All AEs, including nonserious AEs and SAEs, will be collected on the CRF and will be categorized according to the current version (at the time of reporting) of MedDRA. The time period for actively eliciting and collecting AEs and SAEs (“active collection period”) for each participant begins from the time the participant provides informed consent, which is obtained before participation in the study (ie, before undergoing any study-related procedure and/or receiving study intervention), through and including Visit 2 (1 month after vaccination) for AEs, and through and including Visit 3 (6 months after vaccination) for MAEs and SAEs.

Immediate AEs, defined as AEs occurring within the first 30 minutes after study intervention administration, will be assessed and documented on the source documents, on the AE page of the CRF, and on an SAE form as applicable. The time of onset will be recorded for any AEs that occur on the same day as study intervention administration. An MAE is defined as a nonserious AE that results in an evaluation at a medical facility.

If an event is not an AE, then it cannot be an SAE even if serious conditions are met (eg, hospitalization for signs/symptoms of the disease under study, death due to progression of disease).

AEs and SAEs will be captured and reported in accordance with Section 10.3.5 of the protocol.

A 3-tier approach will be used to summarize AEs. Under this approach, AEs are classified into 1 of 3 tiers. Different analyses will be performed for different tiers (see [Section 6.6](#)).

**Tier 1 events:** These are prespecified events of clinical importance and are maintained in a list in the product's Safety Review Plan. There are no preidentified Tier 1 events for this study.

**Tier 2 events:** These are events that are not Tier 1 but are “common”. A MedDRA PT is defined as a Tier 2 event if there are 4 or more participants in at least 1 vaccine group reporting the event. Descriptive summary statistics (counts and proportions) will be provided for Tier 3 events for each vaccine group.

**Tier 3 events:** These are events that are neither Tier 1 nor Tier 2 events.

